#### **Visit 5: Day of Discharge/Postoperative Day 30 ( $\pm 7$ days)**

(1) Collect symptoms and physical examination findings.

(2) Collect laboratory tests, including complete blood count, biomarkers of liver and renal function, etc.

(3) Collect the occurrence of death, RRT, stroke, and paraplegia.

(4) Collect ICU parameters:

- Duration of mechanical ventilation: Time interval between mechanical ventilation and extubation after operation.
- Length ICU of stay: Time interval from ICU admission to transfer or death.
- Collect imaging data, including CTA and echocardiography.

### Visit 6: Postoperative 6 Months ( $\pm 7$ days)

- (1) Collect symptoms and physical examination findings.
- (2) Collect laboratory tests, including complete blood count, biomarkers of liver and renal function, etc.
- (3) Collect imaging data, including CTA and echocardiography.
- (4) Collect the occurrence of death, RRT, stroke, and paraplegia.

### Visit 7: Postoperative 12 Months ( $\pm 7$ days)

- (1) Collect symptoms and physical examination findings.
- (2) Collect laboratory tests, including complete blood count, liver and renal function, etc.
- (3) Collect imaging data, including CTA and echocardiography.
- (4) Collect the occurrence of death, RRT, stroke, and paraplegia.

## Measures to Control Bias

(1) Prospective study design: Subjects and study methods are determined prior to the start of the trial, with all relevant confounding factors included in the statistical analysis. Strict quality control is maintained throughout the study, and all cases that meet the design criteria are included in the final analysis. This approach yields higher-quality and more reliable clinical data and avoids the selection and data processing bias associated with retrospective studies.

(2) Multicenter design: Considering differences in geographic region, hospital, or physician expertise, multicenter case samples are more representative than those from a single center. In addition, multicenter design helps prevent systematic errors from a single center that could bias study results, thereby increasing the credibility of the conclusions. To minimize inter-center variability, all study-related personnel at each center will receive standardized training.

(3) Investigator training: Prior to study initiation, the principal investigators at each center will provide training on the study protocol to ensure that all investigators

are familiar with and understand the surgical procedures for each group.

(4) Standardized application of inclusion and exclusion criteria: Subjects will be screened strictly according to the protocol's inclusion and exclusion criteria, minimizing selection bias.

## Statistical Considerations

### Sample Size

#### Estimation of Total Sample Size

Sample size estimation is performed using PASS 2021 software.

This study adopts a superiority design and a fixed sequence testing strategy. The primary outcome is the incidence of composite events, which is a low-benefit endpoint. The hypotheses are as follows:

- ① Experimental Group 1 is superior to the control group.
- ② Experimental Group 1 is non-inferior to Experimental Group.

The order of hypothesis testing is ①→②. According to the *Guideline on Multiplicity in Clinical Drug Trials*, this strategy will not inflate the overall Type I error rate (FWER), and no adjustment for multiplicity is required.

Based on previous research, the incidence of composite events with mild hypothermic aortic arch clamping combined with bilateral cerebral perfusion is approximately 13.64%, with moderate hypothermic arch clamping combined with unilateral cerebral perfusion is approximately 22.67%, and with the traditional Sun's procedure is approximately 29.63%.

For hypothesis ①, assuming the composite event rate is 13% in Experimental Group 1 and 30% in the control group, with a superiority margin set at 0, a one-sided significance level of 0.025, a power of 80%, and an allocation ratio of 1:1, at least 91 subjects are required in each group.

For hypothesis ②, assuming the composite event rate is 25% in Experimental Group 2 with a non-inferiority margin of 5%, at a one-sided significance level of 0.025, a power of 80%, and an allocation ratio of 1:1, at least 84 subjects are required

in each group.

In summary, taking the maximum required sample size above and allocating subjects in a 1:1:1 ratio among the three groups, and accounting for a 10% dropout rate, a total of 306 subjects will be enrolled in this study, with 102 subjects in each group.

## **Sample Size Allocation and Determination**

This study will be conducted simultaneously in multiple clinical centers. In principle, the number of subjects enrolled per center will be distributed as evenly as possible to ensure adequate center representation. However, considering feasibility and the pace of enrollment, the number of subjects recruited at each participating site may be adjusted to ensure enrollment balance among centers. In any case, the final enrollment at a single center should not exceed 50% of the total sample size.

## **Analysis Populations**

Statistical analyses will be based on clearly defined analysis populations prior to data analysis in this study:

**Full Analysis Set (FAS):** The set constructed according to the intention-to-treat principle, including all subjects who participated in the study and received TAR+FET treatment.

**Per Protocol Set (PPS):** A subset of FAS, including all subjects who completed the trial without major protocol violations.

Baseline data will be analyzed based on the FAS, and analyses of primary and secondary outcomes will be performed on both FAS and PPS.

## **Criteria for Subject Exclusion**

### **FAS Exclusion Criteria**

- (1) Subjects who did not receive TAR+FET treatment after enrollment;
- (2) Subjects with no follow-up records.

## **PPS Exclusion Criteria**

(1) Subjects who violated selection criteria (did not meet inclusion criteria or met exclusion criteria), and such violations substantially affect efficacy or safety assessment;

(2) Subjects in Experimental Groups 1 or 2 (arch clamping combined with bilateral cerebral perfusion) who, for any reason, are switched intraoperatively to conventional TAR+FET (control group) treatment.

In addition to the above criteria, any other conditions that may affect assessment of efficacy or safety will be determined by investigator discussion on a case-by-case basis.

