## **Rationale for Study Design**

- (1) Prospective: Prospective design minimizes bias. Standardized enrollment criteria, methods, process, and outcome measures, clarify the causal relationship.
- (2) Multicenter: Multicenter trials can enroll participants rapidly, resulting in shorter clinical trial periods, good extrapolation, and minimal bias caused by systematic errors.
- (3) Three-arm: This study involves two technical optimizations: temperature change from moderate temperature to mild temperature; unilateral antegrade cerebral perfusion changed to bACP. Due to the inability to control two variables simultaneously using a two-arm design, we plan to establish three groups for a randomized controlled trial.
- (4) Randomized: This trial uses randomization at each center. Each participant successfully screened has equal opportunity and is randomly assigned to Group 1 (arch-clamping technique under mild hypothermia), Group 2 (arch-clamping technique under moderate hypothermia) and Group 3 (Sun's procedure using bilateral antegrade cerebral perfusion) in a 1:1:1 ratio without the investigator nor the participant's personal preferences influence.
- (5) Open-label: The three surgical procedures differ significantly in terms of manipulation, so it is impossible to blind the researchers and participants.
- (6) Parallel-controlled: Sun's procedure as a TAR+FET technique, is the standard surgical treatment for ATAAD.

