## **Subject Selection**

### **Inclusion Criteria**

- (1) Computed tomography angiography (CTA) confirmed as ATAAD according

to the 2022 ACC/AHA Guideline for the Diagnosis and Management of Aortic

Disease; Diagnosis consistent with ATAAD confirmed by aortic CTA;

- (2) Adult patients (18-70 years) weighing 50-120 kg;
- (3) Time interval between the onset of symptoms and operation is less than 14 days;
- (4) Indications for total aortic arch replacement are available;
- (5) Signed informed consent and availability for follow-up.

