#### **Visit 1: Emergency Admission**

- (1) Obtain signed informed consent from the subject.

- (2) Collect medical history and general information.
- (3) Collect symptoms and physical examination findings.
- (4) Collect laboratory tests including complete blood count, liver and renal function, etc.
- (5) Collect ECG and imaging data.
- (6) Verify inclusion and exclusion criteria. Eligible subjects are enrolled and assigned a randomization number, and randomized to Experimental Group 1, Experimental Group 2, or Control Group.

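### Per-protocol exclusions rest on an undefined judgement and on case-by-case decisions by unblinded investigators, so membership of the set can depend on arm and outcome

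*Combined protocol and SAP*

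**What the plan says.** All references are to the combined protocol and SAP.

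- **PPS Exclusion Criteria, rule (1).** A patient who breached an inclusion or exclusion criterion is removed only if "such violations substantially affect efficacy or safety assessment". The rule does not say how large the effect must be, who decides, or when.
- **Rule (2).** Patients in Groups 1 or 2 are removed if they "are switched intraoperatively to conventional TAR+FET (control group) treatment". This is a matter of record and needs no judgement.
- **Closing sentence.** Beyond these two rules, whether anything else that might bear on efficacy or safety removes a patient "will be determined by investigator discussion on a case-by-case basis".
- **Rationale for Study Design, item (5).** Because the operations differ, "it is impossible to blind the researchers and participants".
- **Analysis Populations and Primary Endpoint Analysis.** Both primary tests are run on the FAS and on the PPS. The populations are to be clearly defined before the data are analysed. Neither set is named as decisive.
- **Inclusion Criteria, item (3).** "Time interval between the onset of symptoms and operation is less than 14 days".
- **Visit 1: Emergency Admission.** Criteria are verified here, and then: "Eligible subjects are enrolled and assigned a randomization number, and randomized to Experimental Group 1, Experimental Group 2, or Control Group". The operation is Visit 2.

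**The concern.** A per-protocol set is defensible when its membership follows from rules fixed in advance, or from decisions made without knowledge of arm and outcome. Here neither holds for two of the three routes out of the set. Under rule (1), the same eligibility breach can keep one patient and remove another. Under the closing sentence, the decision lies with investigators who know the arm and who recorded the deaths, renal replacement therapy, strokes and paraplegia at the visits.

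Inclusion (3) adds a smaller problem. It is measured to the operation, so it cannot be confirmed when eligibility is checked and the patient is randomised. A patient properly randomised near day 14 could become an eligibility violator through a delay that arose afterwards, and would then fall under rule (1).

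At stake is the PPS version of both primary tests. Removal that depends on arm and outcome is selection after randomisation, and it can move the estimate in either direction.

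**Working it through.** **Step 1: is there a safeguard elsewhere?**

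- Analysis Populations asks for definition before analysis. That constrains timing, but does not hide arm or outcome from the people who recorded them.
- Database Lock requires two signatures and no population review.
- Protocol Deviations lists attributes of major deviations, but neither PPS rule refers to that list.
- Statistical Analysis Content calls for deviations by type and severity and a breakdown of populations. That is reporting, not adjudication.

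No masked step is described.

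**Step 2: reproduce the plan's sample sizes.** Inputs from Estimation of Total Sample Size: 13% vs 30% for test 1; 25% in Group 2 and a 5-point margin for test 2; one-sided 0.025; power 80%; 10% dropout. The Group 1 rate is not restated for test 2, so 13% is carried over as an assumption.

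n = [1.960·√(2p̄(1−p̄)) + 0.8416·√(p₁(1−p₁)+p₂(1−p₂))]² / δ²

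- Test 1: p̄ = 0.215, δ = 0.17. n = (1.960·0.5810 + 0.8416·0.5684)²/0.0289 = 90.5, so 91.
- Test 2: p̄ = 0.19, δ = 0.12 + 0.05 = 0.17. n = (1.960·0.5548 + 0.8416·0.5483)²/0.0289 = 83.005, so 84.
- Dropout: 91/0.9 = 101.1, so 102.

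The plan's 91, 84 and 102 are reproduced.

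**Step 3: how far does a removal move the decision limit?** The plan names no interval method. The Wald upper limit is used here:

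U = (p₁ − p₂) + 1.96·√(p₁(1−p₁)/n₁ + p₂(1−p₂)/n₂)

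Test 2 passes if U < +5 points; test 1 passes if U < 0. The first case in full: 14/91 − 19/91 = −0.0549; standard error 0.0570; U = −0.0549 + 1.96·0.0570 = +0.0567.

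| Case | Counts | U (points) | Result |
|---|---|---|---|
| Test 2, borderline | 14/91 vs 19/91 | +5.7 | fails |
| one Group 1 event patient removed | 13/90 vs 19/91 | +4.6 | passes |
| one Group 1 event-free patient removed instead | 14/90 vs 19/91 | +5.9 | fails |
| Test 1, borderline | 16/91 vs 27/91 | +0.1 | fails |
| one Group 1 event patient removed | 15/90 vs 27/91 | −0.9 | passes |
| Test 2, planned rates | 12/91 vs 23/91 | −0.8 | passes |
| two Group 2 event patients removed | 12/91 vs 21/89 | +0.8 | passes |
| six removed | 12/91 vs 17/85 | +4.2 | passes |
| seven removed | 12/91 vs 16/84 | +5.04 | fails |

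With 102 per arm at the planned rates (13 vs 26), U = −2.1 points, and ten Group 2 event patients must be removed before test 2 fails. Newcombe limits differ little: −0.6 instead of −0.8 with 91 per arm, and −1.9 instead of −2.1 with 102.

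**Step 4: how often would a result be that close?** Exact binomial enumeration, 102 per arm, Wald, supposing that both removed patients are Group 1 patients with events:

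- At 13% vs 25%, failure of test 2 becomes success in 5.3% of trials, or 3.6% once test 1 must also succeed (control rate 30%).
- At the cited prior rates of 13.64% vs 22.67%, the figure is 9.5% before that requirement.

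These are chances of a close result combined with the worst possible choice of patients. They are not type I error rates.

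**The case against.** Several stronger readings are tempting, and the documents do not support them.

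- **That investigators decide rule (1).** The sentence on investigator discussion covers conditions other than rules (1) and (2). Rule (1) names no judge. The gap there is an undefined judgement, and its test is efficacy or safety, not efficacy alone.
- **That the non-inferiority claim rests on the PPS.** No section gives the PPS priority. The FAS is analysed too and PPS removals cannot alter it, so a changed PPS result would appear as a disagreement between the sets. This is a real protection, although the plan does not say what follows from such a disagreement.
- **That one or two removals would generally flip test 2.** Any result beside a margin turns on one patient, in any trial. The borderline cases above (15.4% vs 20.9% for test 2) are not the planned rates, and they remove only patients with events from one arm. Removing an event-free patient moves the limit the other way.
- **That inclusion (3) will create many violators.** Visit 1 is an emergency admission and Background stresses prompt repair. No interval from randomisation to surgery is given. Only patients near day 14 could be affected.

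It is also fair that limiting PPS removal to breaches that matter is a legitimate design choice. Removing every trivial breach, or redefining eligibility, is not needed to repair this.

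What remains is that the written rules allow selection made with knowledge of arm and outcome, and nothing else in the plan prevents it.

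**Conclusion.** The point holds in limited form. Rule (1) has no threshold, judge or timing. The closing sentence gives all remaining exclusions to investigators in an open-label trial. No masked review is described, so PPS membership can depend on arm and outcome. This is more than missing detail, because the rule as written permits such selection.

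The size is modest. Near the 5-point margin, removing one Group 1 event patient moves the upper limit by about one point (+5.7 to +4.6 with 91 per arm). At the planned rates one or two removals leave test 2 unchanged; seven (91 per arm) to ten (102 per arm) selectively removed Group 2 event patients would be needed to lose non-inferiority. The FAS result is unaffected throughout.

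The figures assume Wald limits, a 13% Group 1 rate in test 2, and worst-case removals. The documents give no basis for estimating how many patients would come up for discretionary exclusion, or how many would pass day 14 after randomisation.

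**What to change.** In PPS Exclusion Criteria:

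1. Replace the condition in rule (1) and the closing sentence with a list, fixed in advance, of the eligibility breaches and other major violations that remove a patient. Apply it identically in all three arms, and judge eligibility on Visit 1 data.
2. Settle any unlisted case before database lock, from a listing prepared by the data manager that hides arm and outcome.
3. State that a delay to surgery arising after randomisation is not by itself a PPS eligibility violation. Inclusion (3) itself need not be reworded for this purpose.

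The cost is a wording change and one masked listing, with slightly less flexibility in defining the PPS. It should be done before outcomes accumulate, since the list cannot credibly be drawn up afterwards. What follows if FAS and PPS disagree is a separate gap that this change does not close.

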## **Statistical Methods**

### **General Principles**

(1) Descriptive statistics: For quantitative variables, the number of cases, mean, standard deviation, median, interquartile range, minimum, and maximum values will be reported. For qualitative variables, absolute and relative frequencies will be reported.

(2) Inferential statistics: Unless otherwise specified, two-sided tests will be used, and a two-sided P-value less than or equal to 0.05 will be considered statistically significant. Comparisons of quantitative data between groups will be performed by analysis of variance or rank-sum test; comparisons of qualitative data will use the chi-square test or Fisher's exact test; multicategorical or ordinal data will be analyzed using the Cochran-Mantel-Haenszel (CMH) test.

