Several observational studies and meta-analyses elaborated that selected antegrade cerebral perfusion reduces the risk of malperfusion and aortic thromboembolism, with lower operative mortality and major complication rates (i.e. strokes and reoperations for bleeding) compared to other arterial cannulation strategies. The EACTS/STS Guidelines for Diagnosing and Treating Acute and Chronic Syndromes of the Aortic Organ recommend that MHCA (26-28°C) deep hypothermic circulatory arrest (20-22°C) for arch surgery in ATAAD [7]. However, using unilateral or bilateral cerebral perfusion remains controversial. Several studies indicate that unilateral and bilateral cerebral perfusion are similar in preventing postoperative neurological dysfunction, while international guidelines recommend using bilateral antegrade cerebral perfusion (bACP) in cases of the prolonged circulatory arrest [7,8]. In 2019, [name] and colleagues from Beijing Anzhen Hospital proposed a novel technical approach for TAR + FET procedure called arch-clamping technique to treat ATAAD. This approach is performed under MHCA (25-28°C), a FET is deployed in the descending aorta and clamped together with the autologous aorta immediately, then distal perfusion was restored via the femoral artery (Figure 1). This approach is easy to manipulate without additional assistive devices, of which the circulatory arrest time is usually limited to about 3 minutes, as well as significantly reducing the CPB duration. The early outcomes showed it was safe and effective in reducing mortality and morbidities. (Table 1) [9,10].

**Figure 1.** A: Conventional TAR + FET procedure; B: Arch-clamping technique.

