**Table 1. The early-outcomes between arch-clamping technique and conventional TAR + FET procedure**

[figure not shown]
Variables	Arch-clamping	Conventional TAR	P value
	Technique (n = 39)	+ FET Procedure (n = 40)	
Circulatory arrest time, (min)	4.1 ± 0.6	23 ± 8.8	0.001
Cross Clamp time, (min)	96.9 ± 4.4	127.1 ± 13.3	0.001
CPB time, (min)	158.4 ± 6.8	198.0 ± 12.6	0.001
Postoperative drainage, (ml) *	465 ± 95.5	440.0 ± 100.5	0.260
Intubation time, (h)	13.6 ± 2.2	34.1 ± 14.3	0.001
Red blood cells transfusion, (U)	4.5 ± 1.5	4.1 ± 1.3	0.210
CRRT, n (%)	1 (2.6)	8 (20)	0.029
Stroke, n (%)	1 (2.6)	2 (5)	0.571
Thirty-day death, n (%)	2 (5)	3 (7.5)	1.000

Values are presented as n (%) or mean ± standard deviation. \* Postoperative 12-hour Drainage; *CPB*, Cardiopulmonary bypass; *CRRT*, Continuous renal replacement therapy.

Our team also try to elevate the core temperature of the circulatory arrest over 28°C. We compared the early outcomes of arch-clamping technique under different temperatures. The results demonstrated that the CPB duration and cross-clamp time were significantly reduced in the mild hypothermia group compared to moderate hypothermia group. Meanwhile, the mild hypothermia group has lower mortality and morbidities, especially for the incidences of stroke, spinal cord injury, and continuous renal replacement therapy (Figure 2) [11]. Our previous studies also found that using bACP as a brain protective strategy can significantly reduce the incidence of permanent neurological dysfunction [12,13]. Therefore, we hypothesize that arch-clamping technique combined mild hypothermia and bACP as a surgical bundle can be effective in minimizing the circulatory arrest time and mitigating multi-organ injury due to temperature changes and prolonged CPB duration.

In summary, we designed a multicenter randomized controlled trial to observe the 30-day and 1-year outcomes of patients with ATAAD after operation, seeking to validate the efficacy and safety of arch-clamping technique under mild hyperthermia

using bACP for the treatment of ATAAD.

**Figure 2.** Postoperative outcomes of using the arch-clamp technique in treating with ATAAD at different temperatures. Cardiopulmonary bypass time and cross-clamp time were presented as minutes; Total hospital stay was presented as days; Other variables were presented as n (%). *CRRT*, Continuous renal replacement therapy.

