## STUDY OBJECTIVES

- (1) To evaluate the validity and safety of arch-clamping technique under mild hypothermia for ATAAD using Sun's procedure with bACP as the comparator.
- (2) To evaluate the validity and safety of arch-clamping technique under mild hypothermia for ATAAD using arch-clamping technique under moderate hypothermia as the comparator.

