## **Secondary Endpoint Analysis**

Analysis of secondary endpoints will be conducted based on both FAS and PPS.

Statistical analysis methods will follow the general principles described above.

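### The secondary times have no named pairwise contrast; a three-group ANOVA would not answer mild versus moderate hypothermia, and its pooled error would badly miscalibrate intervals for arrest and ventilation time

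*Combined protocol and SAP*

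**What the plan says.** All four secondary outcomes are durations: circulatory arrest, cardiopulmonary bypass (CPB), mechanical ventilation and ICU stay. Their inferential plan is one sentence under Secondary Endpoint Analysis: "Statistical analysis methods will follow the general principles described above". Those principles (Statistical Methods, General Principles, item 2) give for quantitative data only "Comparisons of quantitative data between groups will be performed by analysis of variance or rank-sum test", with the criterion that "a two-sided P-value less than or equal to 0.05 will be considered statistically significant".

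Study Objectives sets two pairwise questions about the mild-hypothermia arm: one "under mild hypothermia for ATAAD using Sun's procedure with bACP as the comparator", the other "under mild hypothermia for ATAAD using arch-clamping technique under moderate hypothermia as the comparator".

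Primary Endpoint Analysis spells out these two comparisons, with hypotheses, differences and 95% confidence intervals, but only for the composite. For the times the plan names no contrast, follow-up to an overall test, variance model, effect estimate or interval, and gives no rule for choosing between the two tests.

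**The concern.** In a three-arm trial, a rule that names ANOVA for comparisons between groups is naturally read as one overall test of three means. That test answers neither objective. Groups 1 and 2 share the arch-clamping technique, so a large gap between arch clamping and Sun's procedure is enough to make it significant, whatever temperature does. The question left open is Group 1 against Group 2.

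The second problem is variance. Standard ANOVA assumes a common SD, while Background Table 1 shows the conventional procedure to be far more variable than arch clamping for arrest and ventilation time. If the pairwise comparisons borrow the three-group error term, the noisy control arm inflates the error for Group 1 against Group 2 and the quiet arms dilute it for Group 1 against control.

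The trial is open-label, and the plan leaves the analyst to choose among these readings after the data are seen.

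**Working it through.** **Stated figures.** The plan gives no power or precision for the secondary times. Its sample size concerns the composite: 13% against 30%, one-sided 0.025, 80% power, pooled-variance formula, gives 91 per group, as stated; 91/0.90 = 101.1, so 102 per group and 306 in total, as stated. I use n = 91 per group below; the width ratios are the same at 102.

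**Inputs (Background, Table 1; arch clamping n = 39, conventional n = 40).**
- Circulatory arrest: 4.1 ± 0.6 against 23 ± 8.8 min (SD ratio 8.8/0.6 = 14.7)
- Intubation time, taken as ventilation time: 13.6 ± 2.2 against 34.1 ± 14.3 h (14.3/2.2 = 6.5)
- CPB: 158.4 ± 6.8 against 198.0 ± 12.6 min (12.6/6.8 = 1.85)

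**Assumption.** Background describes arch clamping as introduced at moderate temperature: "This approach is performed under MHCA (25-28°C"). The Table 1 arch-clamping SD is therefore a proxy for Group 2. No Group 1 SD is given; I set it equal to Group 2 and then vary it.

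**Step 1, the overall test.** Let Groups 1 and 2 both have mean arrest time 4.1 min and control 23 min. The pooled variance is (0.36 + 0.36 + 77.44)/3 = 26.05, and the noncentrality is 91 × (18.9² × 2/3)/26.05 ≈ 832. The F test rejected in 100% of 5,000 simulated trials, although Groups 1 and 2 were identical.

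**Step 2, pooled SD** = sqrt((s1² + s2² + s3²)/3).
- Arrest: sqrt(78.16/3) = 5.10 min
- Ventilation: sqrt((4.84 + 4.84 + 204.49)/3) = 8.45 h
- CPB: sqrt((46.24 + 46.24 + 158.76)/3) = 9.15 min

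**Step 3, 95% half-widths.** Pooled: t × pooled SD × sqrt(2/91), with 270 df. Welch: t × sqrt((si² + sj²)/91).

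| Outcome | Pooled | Welch, 1 vs 2 | Ratio, 1 vs 2 | Welch, 1 vs 3 | Ratio, 1 vs 3 | Simulated coverage of pooled interval, 1 vs 3 |
|---|---|---|---|---|---|---|
| Arrest (min) | 1.49 | 0.18 | 8.5 | 1.84 | 0.81 | 89% |
| Ventilation (h) | 2.47 | 0.64 | 3.8 | 3.01 | 0.82 | 89% |
| CPB (min) | 2.67 | 1.99 | 1.34 | 2.97 | 0.90 | 92% |

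Ratios of standard errors alone, without the t quantiles, are 8.5, 3.8 and 1.35 (1 vs 2) and 0.82, 0.83 and 0.90 (1 vs 3). Coverage for 1 vs 2 is about 100%, 100% and 99%.

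**Step 4, what this does to power.** Take, for illustration, a true 1-hour ventilation difference between Groups 1 and 2. The standard error is 2.2 × sqrt(2/91) = 0.326. With the arms' own SDs, power is Phi(1/0.326 − 1.96) = 87%. With the pooled SD the critical difference is 1.96 × 8.45 × 0.148 = 2.46 h, and power is Phi((1 − 2.46)/0.326), effectively 0%.

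**Step 5, vary the Group 1 SD.**
- Arrest, ×0.5 to ×5: 1 vs 2 ratio 10.7 to 2.5; 1 vs 3 ratio stays at 0.81
- Ventilation, ×0.5 to ×5: 4.8 to 1.3; 1 vs 3 stays at 0.82
- CPB, ×0.5 to ×3: 1.57 to 0.94, so the direction reverses; 1 vs 3 runs from 0.91 to 0.85

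ICU stay has no SD in the documents and cannot be checked.

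**Step 6, the other reading.** If ANOVA is run only on the two arms compared, with equal n, its standard error is sqrt(((si² + sj²)/2) × (2/n)) = sqrt((si² + sj²)/n), identical to Welch's. Simulated coverage for 1 vs 3 is then about 95% for all three times.

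**The case against.** The text does not say three-group, overall test or pooled error. A rank-sum test is ordinarily a two-sample test, and the only comparisons the plan writes out, for the composite, are the two pairwise ones. An analyst could run two-arm comparisons within the rule, and Step 6 shows that the distortion then disappears. The plan also promises no intervals for these outcomes, and a bare overall test produces none. All of this stands: the width figures describe one permitted implementation.

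The scale of harm is also limited. For Group 1 against control, the Table 1 differences are 18.9 min, 20.5 h and 39.6 min, against half-widths of at most 1.84 min, 3.01 h and 2.97 min, so under-coverage would not alter a conclusion. For Group 1 against Group 2, the only one of these times for which Background reports a temperature effect is CPB, where the distortion is smallest. The documents name no arrest-time difference of interest on the scale of ±0.18 against ±1.49 min. These are secondary outcomes with no sample-size claim.

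The objection does not supply the missing contrasts. Nothing carries the composite's pairwise tests over to the times, and a rule that can be read in two ways with such different results needs to say which is meant.

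**Conclusion.** The gap is real: both objectives are pairwise, no pairwise contrast is named for the secondary times, and the most natural reading of the rule leaves mild against moderate hypothermia unanswered. The equal-variance assumption behind ANOVA is contradicted by Table 1 for arrest and ventilation time. The large interval errors, about 8.5 and 3.8 times too wide for Group 1 against Group 2, are conditional on the three-group pooled error and on an assumed Group 1 SD; the direction holds across the range tried, the size does not.

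A reader might infer that the plan commits to a three-group pooled analysis, that all four times are badly affected, or that the comparison with control would mislead. The documents support none of these. The error term is unstated, CPB is affected modestly and may reverse, ICU stay cannot be assessed, and the control comparison is robust at differences as large as Table 1's. The practical risk lies with Group 1 against Group 2. This should be corrected; it does not touch the primary analysis.

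**What to change.** In General Principles (2) and Secondary Endpoint Analysis, state that each time outcome is analysed by two contrasts, Group 1 minus control and Group 1 minus Group 2, each using only the two arms concerned and reported with a 95% confidence interval. Use the Welch unequal-variance t for the mean difference, or the rank-sum test with the Hodges-Lehmann difference where the time is expected to be skewed. Assign the method to each outcome by name now, so that the choice does not depend on the trial data. If an overall three-group test is kept, label it descriptive and do not make the contrasts depend on it.

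The cost is wording in two sections. Sample size, conduct, data collection and the primary test are unchanged.
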